Randomization will be stratified by presence/absence of DO on the initial cystometry. A balanced randomization scheme will be generated with equal numbers of placebo and lidocaine. Identically appearing study drug syringes will be placed in consecutively numbered opaque envelopes by an unmasked study coordinator not participating in the procedure visit or study analyses. Both the urodynamic nurse and patient will be blinded to the type of lubricant. After randomization, the urethral catheter will be removed and 5mL of either placebo or 2% lidocaine will be injected into the urethra. The patient will sit for 5 minutes to allow lidocaine to take anesthetic effect. The catheter is then replaced, and cyostometry and PFS will be repeated. A continuous pain scale from 0 to 100 (visual analog scale) will be used by the patient to report her pain level during cystometry #1 (during catheter insertion and at maximum cystometric capacity), PFS #1, overall UDS #1, cystometry #2 (during catheter insertion and at maximum capacity), PFS #2, and overall UDS #2 discomfort. At the end of the procedure, the urodynamic nurse will also provide a subjective assessment of patient discomfort.

Planned Analyses & Power Calculation:

The primary outcome is the volume at which a participant perceives a strong desire to void. Statistical analyses will estimate the confidence interval for this outcome measure between the two arms of the study (i.e., using 2% lidocaine vs. aqueous jelly) through the standard calculation for the difference in means when standard deviations of the two arms are unknown, i.e., through the Student's t distribution. As it is thought that there will be no difference in the mean value of the two arms, the study will be designed as an equivalence trial. Since DO may alter findings, it is planned to stratify the randomization for DO in order to insure a balance between the arms for this variable. Prior to randomization, each patient will undergo a

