baseline standard cystometry without lidocaine, and DO (present or absent) will be obtained from this evaluation. The observations from this *baseline cystometry* provide for an interesting and novel analysis: the baseline measure of volume at strong desire to void may serve as a covariate to adjust for individual patient variability. That is, comparisons of the difference in the baseline measure and the experimental measure will provide a patient "standardized" evaluation of her additional volume following the baseline. Analysis of the primary outcome will account for patient variability with standardization by the value of the baseline measure.

Beyond the primary outcome cystometric evaluations are numerous secondary outcomes such as pain/discomfort with filling and emptying, presence/absence of DO, and emptying metrics including flow rates, post-void residual, EMG activity, and detrusor pressures (max and at peak flow). Continuous measures will use the Student's t distribution as with the primary outcome. Binary and ordinal outcomes will be evaluated using logistic regression. The use of logistic regression for the ordinal outcomes is through the proportional odds model and combines with the cumulative logit link. All of these evaluations may incorporate the baseline urodynamic study metrics as a covariate (as described above for the primary outcome).

Assuming an average strong desire to void during cystometry (with plain lubricant gel) of 300mL, standard deviation of 100mL (3, 5), a non-inferiority margin of 75mL (i.e., 25% of 300mL), Power (1- β) of 0.80 and α of 5%, **31 participants per study arm** (i.e., 62 total) are needed to demonstrate "equivalence" in sensation during cystometry using plain lubricant gel versus lidocaine gel. Allowing for 12% participants being unable to complete the second half of the UDS, a total of **35 participants per study arm** (i.e., **70 total participants**) will be enrolled.

In the placebo group, the data from the two filling cystometry tests can be compared (sensation metrics, DO presence/absence, and compliance) to establish "normal variability". Anecdotally, patients commonly tolerate a second fill better. With this normal variability better

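### The primary analysis is committed to baseline adjustment but described both as a covariate and as a difference from baseline; one named ANCOVA would settle it, at a cost of at most about one power point

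*Combined protocol and SAP*

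**What the plan says.** All of this is in the combined protocol and SAP, section Planned Analyses & Power Calculation.

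- **Base method.** The primary outcome, volume at strong desire to void, is compared between arms by a Student's t confidence interval, "through the standard calculation for the difference in means when standard deviations of the two arms are unknown".
- **Covariate.** "the baseline measure of volume at strong desire to void may serve as a covariate to adjust for individual patient variability".
- **Difference.** The next sentence opens as an explanation of the covariate sentence: "comparisons of the difference in the baseline measure and the experimental measure will provide a patient" standardized evaluation of her additional volume after the baseline.
- **Commitment.** "Analysis of the primary outcome will account for patient variability with standardization by the value of the baseline measure".
- **Carry-over to secondary outcomes.** "All of these evaluations may incorporate the baseline urodynamic study metrics as a covariate (as described above for the primary outcome").
- **Sample size.** It uses an SD for a single fill: "standard deviation of 100mL (3, 5), a non-inferiority margin of 75mL", with 80% power and an alpha of 5%, giving 31 per arm.
- **Stratification.** "Since DO may alter findings, it is planned to stratify the randomization for DO". The stratum does not appear in any stated analysis of the primary outcome.

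The Abstract, which compares variation between the two tests across arms, fits the difference. The secondary-outcome paragraph refers back to the primary method as a covariate.

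**The concern.** The plan says that adjustment will be done and then leaves open which adjustment. A covariate model estimates from the data how much of the baseline to subtract. A difference from baseline fixes that slope at 1. Under randomization both estimate the same arm effect in mL without bias, so no bias needs correcting. What differs is the standard error.

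In an equivalence trial the whole interval must lie inside the margin, so the same data can pass under one analysis and fail under the other. The sample size was worked out for neither: it rests on the SD of one fill. Whether the difference analysis has more or less power than planned depends on a correlation that the documents do not give. The secondary outcomes inherit the ambiguity through their cross-reference.

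**Working it through.** **Inputs from the plan:** SD 100 mL, margin 75 mL, 31 evaluable per arm, power 0.80, alpha 5%, equivalence design, no true difference expected.

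**Assumed, because the documents are silent:** rho between fills, and the second-fill SD (SD2). The first-fill SD (SD1) is set to 100 mL. The plan does not say how the 5% is split; 5% for each of two one-sided tests is the reading that reproduces its sample size.

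**Step 1: reproduce the plan's figure.** With 5% per one-sided test and beta shared between the two tests:

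n per arm = 2 × [100 × (1.645 + 1.282) / 75]² = 30.4, rounded up to **31**. This agrees with the plan. At 2.5% per test the same formula gives 38.

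**Step 2: the SD behind each analysis.**

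- Unadjusted second fill: SD2, 60 df.
- Difference: √(SD1² + SD2² − 2·rho·SD1·SD2), 60 df. With equal SDs this is 100·√(2(1 − rho)).
- ANCOVA: SD2·√(1 − rho²), with the variance multiplied by 1 + 1/58 for estimating the slope, 59 df.

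**Step 3: power and interval width.** Power is exact for two one-sided t tests at 5% each, integrated over the distribution of the sample variance. The typical 90% CI half-width is t × SD × √(2/31), with t = 1.671. For the unadjusted comparison it is 1.671 × 100 × 0.254 = 42.4 mL, with power **0.797**.

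With SD 100 mL at both fills:

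| rho | Difference: SD, half-width (mL) | Power | ANCOVA: SD, half-width (mL) | Power |
|---|---|---|---|---|
| 0 | 141.4, 60.0 | 0.325 | 100.0, 42.8 | 0.788 |
| 0.3 | 118.3, 50.2 | 0.589 | 95.4, 40.8 | 0.835 |
| 0.5 | 100.0, 42.4 | 0.797 | 86.6, 37.1 | 0.910 |
| 0.7 | 77.5, 32.9 | 0.966 | 71.4, 30.6 | 0.984 |
| 0.8 | 63.2, 26.8 | 0.997 | 60.0, 25.7 | 0.998 |

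**Step 4: vary the second-fill SD.** Power at rho 0.3, 0.5 and 0.7:

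| SD2 (mL) | Unadjusted | Difference | ANCOVA |
|---|---|---|---|
| 80 | 0.955 | 0.713, 0.876, 0.984 | 0.968, 0.989, 0.999 |
| 120 | 0.569 | 0.439, 0.671, 0.912 | 0.623, 0.746, 0.917 |

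The difference beats the unadjusted comparison once rho exceeds SD1/(2·SD2): 100/160 = 0.63, 100/200 = 0.50 and 100/240 = 0.42 for SD2 of 80, 100 and 120 mL.

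**Step 5: where ANCOVA loses.** At rho 0 it trails the unadjusted test (0.788 against 0.797 at SD2 100; 0.557 against 0.569 at SD2 120). Where the best slope, rho·SD2/SD1, is close to 1, it can trail the difference: at SD2 120 and rho 0.8 the slope is 0.96 and power is 0.982 against 0.984.

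**Step 6: the DO stratum.** If DO is unrelated to volume, adding it changes ANCOVA power by about 0.001. If women with DO (30% assumed) reach strong desire 60 mL sooner at both fills (also assumed), it adds 0.011, 0.004 and 0.000 at rho 0.3, 0.5 and 0.7.

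**The case against.** The strongest reply is that the section can be read coherently. It names a Student's t interval, and the explanatory sentence turns the covariate remark into a comparison of differences, so the plan may simply mean a two-sample t interval on each woman's change. Naming that analysis would also end the ambiguity. Much of this stands: a method is named, and the difference is a valid analysis. But the word covariate is used twice, once to describe the primary method after the fact, and nothing in the text chooses.

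A reader might infer more than the documents support:

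- **A third, ratio-type analysis.** Standardization by the baseline could suggest dividing by it, off the mL scale of the margin. The preceding sentence defines the standardized quantity as additional volume, so it most naturally repeats the difference.
- **An underpowered trial.** The 0.589 at rho 0.3 is one assumed case. Both fills are in the same woman at the same visit, and nothing in the documents favours 0.3 over 0.7. With equal SDs the difference meets the unadjusted 0.797 at rho 0.5 and exceeds it above that.
- **A defect in leaving DO out of the model.** Stratified randomization already balances DO, and the precision gain is probably small.

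**Conclusion.** The point holds as an unresolved choice between two adjusted estimators, and it should be fixed before analysis. It is neither a bias nor a demonstrated shortfall in power.

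Under the equal-SD assumption, ANCOVA gains 0.246 in power over the difference at rho 0.3 (0.835 − 0.589), 0.113 at 0.5 and 0.018 at 0.7. Against the unadjusted 0.797, the difference falls short only if rho is under 0.5. ANCOVA is at least as precise as either alternative, apart from a loss of about one power point near rho 0 or, against the difference, where the slope is close to 1. So it is not entirely free in power, and it does not guarantee 80%: with a second-fill SD of 120 mL its power is 0.746 at rho 0.5.

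The absolute powers rest on 5% per one-sided test and 31 evaluable per arm. At 2.5% per test the ranking is the same: ANCOVA 0.711 against 0.380 for the difference at rho 0.3, and 0.961 against 0.925 at rho 0.7.

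**What to change.** Replace the three adjustment sentences (covariate, difference, standardization) with one primary model:

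- **Model.** ANCOVA of the cystometry #2 strong-desire volume on arm, cystometry #1 strong-desire volume and DO stratum (present/absent). DO is included because randomization is stratified by it.
- **Decision.** Declare equivalence if the 90% CI for the adjusted mean difference, in mL, lies within −75 to +75 mL. This is 5% per one-sided test, the level that reproduces 31 per arm.
- **Sensitivity analyses.** Report the difference from baseline and the unadjusted second-fill comparison.
- **Sample size.** Leave it at 31 evaluable and 35 enrolled per arm.

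The aim in Background of the Problem, that each woman serves as her own control, is kept: with baseline in the model, the arm effect and its CI are identical whether the outcome is the second volume or the change. The secondary-outcome cross-reference then points to a defined model.

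The cost is wording only. Baseline volume and DO status are already recorded before randomization, so no extra patients or procedures are needed.

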Lessons on Urethral Lidocaine in Urodynamics ("LULU"): Impact of intraurethral lidocaine on cystometric parameters and discomfort, a RCT

NCT04038099

11/22/2019

Lessons on Urethral Lidocaine in Urodynamics ("LULU"): Impact of intraurethral lidocaine on cystometric parameters and discomfort, a RCT

Abstract

Complex cystometric studies are often conducted to assess for and clarify incontinence. In current practice, intraurethral aqueous jelly is used to lubricate and insert urethral catheters for these studies. Patients commonly complain of urethral discomfort and/or pain with catheter insertion. Two percent lidocaine jelly has not been routinely used in practice for cystometric catheter insertion due to the unknown impact it may or may not have on complex cystometric parameters. Previous studies evaluating the use of 2% lidocaine jelly for office cystoscopy have not proven to consistently provide substantial relief of discomfort. However, a recent study using 2% lidocaine jelly for catheter insertion during complex cystometric evaluation did demonstrate significant relief of discomfort. Some studies have evaluated 2% lidocaine jelly use during complex cystometric evaluation in neurogenic populations, indicating a surprising increase in detrusor overactivity with 2% lidocaine jelly use. However, few studies have evaluated the impact of 2% lidocaine jelly in a non-neurogenic population. If use of 2% lidocaine jelly was found to improve discomfort during complex cystometric studies in this patient population without substantially altering the study's findings, this could impact clinical practice in an important way. Herein, we propose a randomized, double blind, controlled trial for patients undergoing complex cystometric evaluation. Patients will undergo routine complex cystometric evaluation for acquisition of baseline data using a small amount of intraurethral aqueous jelly for catheter lubrication. Then, they will be randomized to instillation of either placebo (additional intraurethral aqueous jelly, 5ml) or intraurethral 2% lidocaine jelly. Participants then undergo complex cystometry a second time. Normal variations in studies with placebo will be compared to variations within the 2% lidocaine jelly group to determine if

cystometric parameters are altered in any clinically important ways. Patient discomfort will also be evaluated by both the patient and the urodynamics advanced practice nurse.

Purpose of Study

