defined, we will be able to assess for changes attributable to the lidocaine in the group receiving the anesthetic jelly—specifically, whether volume of first sensation or bladder capacity is altered. We can also assess lidocaine's impact on bladder emptying by comparing voiding metrics. In patients with repetitive DO on their first cystometry, we will be able to assess whether they continue to demonstrate DO on their second cystometry with lidocaine.

Primary Outcome: Assess whether use of intraurethral 2% lidocaine jelly meaningfully impacts sensation during filling (specifically, strong desire to void).

Secondary Outcomes: Determine whether the use of intraurethral 2% lidocaine jelly meaningfully impacts the following:

Pain/ Discomfort

- 1. Measured by a visual analog scale during cystometry (catheter insertion and at maximum cystometric capacity), during PFS, and post-procedure
- 2. Provider perception of patient discomfort

Filling Metrics (besides sensation)

- 3. Presence/ absence of detrusor overactivity (DO)
- 4. Compliance ($\Delta Volume / \Delta P_{det}$)

Voiding Metrics

- 5. Maximum flow rate (mL/sec)
- 6. Voiding pattern: normal, intermittent, interrupted
- 7. Detrusor void (yes/no) vs. Valsalva vs. mixed void
- 8. Voided volume and post-void residual (mL)
- 9. Voiding efficiency, i.e., voided volume/ (voided volume + PVR) (3)

- 10. P_{det}max (cm H₂O)
- 11. P_{det}peak flow (cm H₂O)
- 12. EMG activity

Participant Eligibility

Inclusion Criteria	Exclusion Criteria
Female patients	Diagnosis of pelvic pain, interstitial cystitis, or bladder pain syndrome
>18 years of age	Known neurogenic disease impacting voiding/ continence (e.g., Parkinson disease, multiple sclerosis, myasthenia gravis, recent stroke)
Already scheduled (or being scheduled) for UDS to assess urinary incontinence	Active UTI
Able to speak and read in English	Pelvic organ prolapse that is unable to be easily reduced
	Pregnancy or breastfeeding
	Allergy or hypersensitivity to lidocaine or local anesthetics

Ethical Conduction

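### For first sensation and bladder capacity, change is attributed to lidocaine through an undefined placebo benchmark, and the plan does not say whether this or the randomised between-arm comparison decides

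*Combined protocol and SAP*

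**What the plan says.** Planned Analyses & Power Calculation sets out a randomised comparison. For strong desire to void, "Statistical analyses will estimate the confidence interval for this outcome measure between the two arms of the study", by Student's t. Continuous secondary measures follow the same method, and binary and ordinal ones use logistic regression. Baseline values are an optional covariate for the secondary outcomes.

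The closing paragraph of that section adds a second route. In the placebo group "the data from the two filling cystometry tests can be compared" on sensation metrics, DO and compliance, to establish normal variability. The stated background is an expected repeat-fill effect: "Anecdotally, patients commonly tolerate a second fill better". Once that variability is known, "we will be able to assess for changes attributable to the lidocaine in the group receiving the anesthetic jelly", with first sensation and bladder capacity named as the measures in question. A further sentence says that in women with repetitive DO at the first fill, persistence of DO at the second fill with lidocaine can be assessed. It mentions no placebo comparator.

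The Abstract puts the idea differently: "Normal variations in studies with placebo will be compared to variations within the 2% lidocaine jelly group to determine if" cystometric parameters change in clinically important ways.

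Purpose of Study lists first sensation and maximum capacity among the measures on which a change above 25% would be meaningful. The numbered Secondary Outcomes list leaves them out, because its filling metrics are limited to those other than sensation.

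**The concern.** Two routes lead to a statement that lidocaine did or did not alter a filling measure, and they can disagree on the same data. The randomised contrast removes anything that both arms share, including the repeat-fill effect that the plan itself expects. The benchmark route has no test, threshold, interval or alpha. Read as a within-group judgement against a placebo yardstick, it can ignore the sampling error of a yardstick built on about 31 women. It can also mistake a shared repeat-fill shift for a drug effect, or be so wide that it finds nothing. Whether lidocaine leaves filling findings intact is the practice question of the trial, and the choice of route could be made after the data are seen. The DO persistence sentence has a similar weakness, since some resolution on a second fill is expected without any drug effect.

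**Working it through.** **Inputs from the plan.** Mean 300 mL, SD 100 mL, margin 75 mL, power 0.80, alpha 5%, 1:1 allocation, 31 per arm completing. All are given for strong desire to void.

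**Assumptions.** The SD of 100 mL and the 75 mL effect are borrowed for first sensation and capacity. The documents give neither the fill-to-fill correlation ρ (taken as 0.3 to 0.7) nor the size of the repeat-fill shift (taken as 0 to 50 mL, equal in both arms).

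**Plan's own figure.** Two one-sided tests at 0.05 each, true difference 0: n = 2 × [100 × (1.645 + 1.282) / 75]² = 30.45, so 31 per arm. This reproduces the plan and is not in question.

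**SD of the fill-1-to-fill-2 change.** 100 × √(2(1 − ρ)) = 118, 100 and 77 mL for ρ = 0.3, 0.5 and 0.7.

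**False positives with no lidocaine effect, by reading of the benchmark text:**

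1. *Placebo mean change as a fixed benchmark.* The standard error used is too small by a factor of √2, so the rate is 2 × P(Z > 1.96/√2) = 16.6%. Simulation gives about 16% at every shift and correlation.
2. *Significant change in lidocaine but not in placebo.* If p is the chance that one arm's paired test rejects, the rate is p(1 − p).
   - No shift: 0.05 × 0.95 = 4.75%.
   - ρ = 0.5, shift 25 mL: 0.271 × 0.729 = 19.8%.
   - ρ = 0.7, shift 30 mL: 0.551 × 0.449 = 24.7%.
   - The ceiling is 0.5 × 0.5 = 25%. With a 50 mL shift, a true 75 mL effect is detected only about 7% to 38% of the time, because placebo also tends to be significant.
3. *Lidocaine mean change outside the placebo individual range.* The limits lie 1.96 × 100 = 196 mL either side of the placebo mean at ρ = 0.5. False positives are about 0%, but a true 75 mL effect is flagged under 1% of the time.
4. *Between-arm comparison of change.* About 5% throughout.

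**Between-arm options, power for a true 75 mL difference (two-sided 5%, 31 per arm):**

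| Analysis | Standard error, ρ = 0.3 / 0.5 / 0.7 (mL) | Power |
|---|---|---|
| Second fill, unadjusted: 100√(2/31) | 25.4 / 25.4 / 25.4 | about 83% |
| Change score: 100√(2(1 − ρ))√(2/31) | 30.1 / 25.4 / 19.7 | 69% to 97% |
| Second fill adjusted for first (ANCOVA): 100√(1 − ρ²)√(2/31) | 24.2 / 22.0 / 18.1 | 85% to 98% |

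All three hold 5%. The simulated ANCOVA has no DO stratum term.

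**DO persistence.** Suppose 6 to 12 of 31 lidocaine women have DO at the first fill and 70% to 90% would persist with no drug effect (both assumed). The chance that at least one resolves is then between 1 − 0.9⁶ = 47% and 1 − 0.7¹² = 99%. Resolution in the lidocaine arm alone is therefore no evidence of a drug effect.

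**The case against.** The strongest reply is that there may be no competing route at all. The Abstract sets placebo variation against lidocaine-group variation, which can simply mean comparing change between arms, and that holds 5%. The section also describes the difference between baseline and experimental values as the standardised measure for the primary outcome. Placebo is brought in precisely to account for the easier second fill, and nothing in the text tells the analyst to test each arm separately. The general rule for continuous measures is broad, and the secondary outcomes there are introduced as examples, so first sensation and capacity may fall under it. The wording is permissive, and no alpha is assigned to secondary measures.

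Most of this stands, and it limits what can be said. A reader might infer that the plan fails to hold 5% error. The documents do not support that, because they state no decision rule and one permitted reading does hold it. A reader might also infer that DO and compliance are to be judged by the benchmark. Both are numbered secondary outcomes with a between-arm method, compliance appears only in the placebo comparison, and the attribution sentence names neither.

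The reply does not show which route decides. The only sentence that names first sensation and capacity in an analysis places the assessment within the lidocaine group, after the placebo yardstick is set.

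**Conclusion.** The point holds for first sensation and bladder capacity. Their attribution rule is undefined, and under several natural readings it departs from 5% in one direction or the other: about 16%, about 5% to 25%, or about 0% with almost no power. Under a between-arm reading it is 5%. These figures rest on the borrowed SD and on assumed correlations and shifts. The 16% depends on neither correlation nor shift; the 5% to 25% range depends on both. The DO persistence sentence needs a comparator, but DO itself already has one in the planned logistic regression. A reader might extend the concern to the trial's main conclusion. That is not supported: strong desire to void has a stated between-arm confidence interval, and the 31 per arm reproduces. This is a free improvement to the secondary analyses.

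**What to change.** Replace the attribution sentence at the end of Planned Analyses & Power Calculation with a statement that change is attributed to lidocaine only by the randomised between-arm contrast.

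- **First sensation, first desire, maximum capacity and compliance:** regress the second-fill value on arm, the same measure at the first fill, and the DO stratum. Report the adjusted difference with its confidence interval.
- **DO:** use the logistic model already planned, with arm and baseline DO, so that persistence is compared between arms and not read in the lidocaine group alone.
- **Placebo first fill versus second fill:** keep as a description of repeatability, with no role in deciding whether lidocaine altered a measure.
- **Abstract:** align the sentence on placebo and lidocaine variation with this rule.

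The cost is wording only. All the measurements are already collected, and the sample size does not change.
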